2.4.2 Prior, concomitant and post therapies

Prior medications are defined as medications taken by trial subject and the use was stopped prior to first dose of study treatment. Prior and concomitant medications, and post therapies will be summarized and listed based on SAF set.

Prior medications for CSU will be summarized separately by type of therapy (i.e. Sedating H1-antihistamines, Non-sedating H1-antihistamines at licensed dose, Non-sedating H1-antihistamines at up to 4x licensed dose, H2-Antihistamines, Omalizumab, Leukotriene receptor antagonist, Cyclosporine, Other immunosuppressants, Oral corticosteroids, Dapsone, Anti-inflammatory drugs, Anti-depressants (doxepin)) and preferred term. Prior medications non-related to CSU will be summarized by Anatomical Therapeutic Chemical (ATC) code and preferred term.

Concomitant medications categorized as “General (Non-CSU related)” and “CSU related”, and significant non-drug therapies prior to and after the start of the study treatment will be listed. Concomitant medication for CSU categorized as “Background Medication” will be summarized by preferred term. Concomitant medication for CSU categorized as “Rescue” will be summarized by medication type (H1-antihistamin, Oral corticosteroids), ATC and preferred term. Furthermore, concomitant medication for Non-CSU will also be summarized according to the ATC classification.

2.5 Analysis of the primary objective

The primary objective of this study is to investigate the safety and tolerability of ligelizumab 120 mg q4w for 12 months.

2.5.1 Primary endpoint

The primary variable is the number and percentage of patients who reported treatment emergent adverse events during the 64 week study period.

All adverse events which start after the first dose of study medication and within 16 weeks of the last dose will be considered as a treatment emergent adverse event.

2.5.2 Statistical hypothesis, model, and method of analysis

The number of subjects who had a treatment emergent adverse event (events which started on or after the first dose of study treatment and within 16 weeks after the last study treatment, or events present prior to the first dose of study treatment but increased in severity based on preferred term within 16 weeks after the last study treatment) will be summarized overall, by system organ class (SOC) and preferred term descriptively. No statistical model will be applied for the primary endpoints.

All information obtained on adverse events will be displayed by subject.

All treatment emergent adverse events (TEAEs) during treatment period will also be summarized separately.

In addition to what is described in the primary endpoints section, treatment emergent adverse events with the number and percentage of patients having any adverse event overall, by system organ class and preferred term will be provided for:

- Serious treatment emergent adverse events (TESAEs)
- TEAEs by maximum severity
- TEAEs suspected by the investigator as study drug related
- TEAEs leading to permanent discontinuation of study drug

The number of subjects with TEAEs of special interest will be listed and summarized.

A subject with multiple adverse events within a primary system organ class is only counted once towards the total of the primary system organ class.

Unless otherwise specified, primary system organ classes will be sorted alphabetically and, within each primary system organ class, the preferred terms will be sorted in descending order of frequency. If a patient reported more than one adverse event with the same preferred term, the adverse event will be counted only once. If a patient reported more than one adverse event within the same primary system organ class, the patient will be counted only once at the system organ class level.

In addition, the most frequent TEAEs will be presented by preferred term in descending order of frequency.

For TEAEs by maximum severity, missing severity will be assumed to be severe in the summary table.

2.5.3 Handling of missing values/censoring/discontinuations

For the subject who discontinued treatment or study, no imputation or adjustment will be considered for counting the number of subjects who have a treatment emergent AE/SAE. All subjects will be treated equally when the data is summarized, regardless of the treatment duration and/or study duration of each subject.

2.5.4 Supportive analyses

No supportive analyses are planned.

2.6 Analysis of secondary efficacy objective(s)

All efficacy variables (UAS7, HSS7, ISS7 and DLQI) will be analyzed in the SAF.

2.6.1 Secondary endpoints

Each endpoint of efficacy variables (UAS7, HSS7, ISS7 and DLQI) are as follows.

- Absolute change from baseline of UAS7, ISS7 and HSS7
- Proportion of subjects with HSS7 = 0, ISS7 =0 and UAS7=0 response
- Time to achievement of complete UAS7 response (UAS7 = 0), time to achievement of UAS7 \leq 6 response

- Time to loss of complete UAS7 response ($UAS7 = 0$) from Week 52 for patients have achieved complete $UAS7 = 0$ response at Week 52
- Time to $UAS7 \geq 16$ for patients having achieved $UAS7 \leq 6$ at week 52
- Absolute change from baseline of DLQI
- Proportion of subjects with $DLQI = 0/1$

2.6.2 Statistical hypothesis, model, and method of analysis

No formal statistical analysis will be provided.

Summary tables will be presented by visit or week using descriptive statistics. Categorical variables will be presented as frequencies and percentages. For continuous variables, mean, standard deviation, median, minimum, and maximum will be presented. Mean the change from baseline (UAS7, HSS7, ISS7 and DLQI) will be shown descriptively with 95% confidence interval based on one-sample t-test. Proportion of subjects ($UAS7=0$, $HSS7=0$, $ISS7=0$ and $DLQI=0/1$) will also be shown with 95% confidence interval based on the Clopper-Pearson (exact) method. All analyses will be provided descriptively and no formal statistical testing will be applied. Figures will also be provided. The $UAS7=0$ response status will be defined based on the weekly UAS7 score by week. For instance, if the observed $UAS7=0$ at week 12, it will be considered as response, otherwise it is considered as a non-response unless UAS7 is missing. No non-responder imputation is planned in this study.

For time to achievement of complete UAS7 response, Kaplan-Meier estimator will be used to estimate the cumulative incidence function and the results will be plotted. Only the treatment period will be included in this time to first response analysis. Time to first complete $UAS7 = 0$ response achievement will be considered censored at the date of the last non-missing weekly score for any patient who is a non-responder. For the time to achievement of $UAS7 \leq 6$ response analysis, the patients with baseline $UAS7 \leq 6$ response will be excluded from the analysis as well.

For subjects who completed 52 week treatment period, time to loss of complete UAS7 response from Week 52 will be analyzed using Kaplan-Meier estimator similarly as the time to achievement of complete UAS7 response analysis. Time to first loss of complete UAS7 response from Week 52 for patients having achieved complete $UAS7=0$ response at Week 52 will be considered censored at the date of the last non-missing weekly score for any patient who remains as a responder. Time to loss of response analyses will be based on post-treatment follow-up period.

Time to $UAS7 \geq 16$ for patients having achieved $UAS7 \leq 6$ at week 52 will be performed in a similar way as the time to loss of complete UAS7 response analysis.

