9.1 Discontinuation

9.1.1 Discontinuation of study treatment

Discontinuation of investigational treatment for a subject occurs when investigational treatment is stopped earlier than the protocol planned duration, and can be initiated by either the subject or the investigator.

The investigator must discontinue investigational treatment for a given subject if, he/she believes that continuation would negatively impact the subject's well-being.

Investigational treatment must be discontinued under the following circumstances :

- Subject decision
- Adverse events for which continued exposure to the study drug would be detrimental
- Abnormal renal laboratory results requiring discontinuation (see [Section 16.3](#) Appendix 3)
- Abnormal liver laboratory results requiring discontinuation (see [Section 16.2](#) Appendix 2)
- Platelets < 75,000/ μ L

- Pregnancy (See [Section 8.4.4](#) and [Section 10.1.4](#))
- Subject develops a medical condition that requires use of prohibited treatment as per [Section 6.2.2](#), or if subject exhibits a behavior of non-compliance regarding prohibited medications
- Subject received a live virus vaccination during the study
- Subject experiences an unexpected hypersensitivity reaction of grade 5, as defined by the World Allergy Organization Grading System ([Cox et al 2017](#)), see [Section 16.6](#) Appendix 6:
 - Lower or upper respiratory: Respiratory failure with or without loss of consciousness; or
 - Cardiovascular: Hypotension with or without loss of consciousness
- Emergency use of epinephrine due to anaphylactic or anaphylactoid reaction
- Any other protocol deviation that results in a significant risk to the subject's safety
- Any situation in which study participation might result in a safety risk to the subject
- If a subject uses rescue oral corticosteroids for CSU more than 3 doses in a 30 day period or more than 9 doses of in total after week 12 during the study period (including the follow-up period).

If discontinuation of investigational treatment occurs, the investigator should make a reasonable effort to understand the primary reason for the subject's premature discontinuation of study treatment and record this information. Always consider reasons which are related to safety and efficacy first.

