3.1 Primary endpoint(s)

No formal statistical power calculations to determine sample size were performed for this study. The sample size is determined based on the regulatory requirement by Pharmaceuticals and Medical Devices Agency (PMDA) to fulfill the long term safety data for Japanese patients. Considering 10% drop out rate based in the QGE031C2201 study, the planned sample size (N=65) in this study will have 58 patients with 1 year exposure, and it is expected to have 100 Japanese patients exposed to ligelizumab with 1 year in the total ligelizumab CSU program, together with QGE031C2201/E1 and QGE031C2303 studies. With the total sample size (N=100) exposed to ligelizumab in Japanese patients, one can expect to see at least one patient with a specific AE with 95% probability, assuming the occurrence rate of an AE is 3%, aligned with ICH E1 guideline. Safety data from the study will also be evaluated together with Japanese patients from other ligelizumab studies in the submission dossier.

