5.1 Derivation rules for end of treatment date

The end of treatment date up to Week 52 treatment period is defined as below.

1. If patients complete treatment period, the end date is the first non-missing date of the following dates: Week 52 dosing date, Week 52 visit date, PD date of missing visit at Week 52, first dosing date + 52 weeks.
2. If patients early discontinue treatment before Week 52, the end date is the first non-missing date of the following dates: last dosing date + 4 weeks, last visit date, PD date of missing visit at Week 52, first dosing date + 52 weeks.

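### The time-to-first-response curve is labelled a cumulative incidence but censors non-responders who stop treatment, so it sits at or somewhat above the share of patients who respond on treatment

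*SAP*

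**What the plan says.** SAP 2.6.1 lists time to first UAS7 = 0 and time to first UAS7 ≤ 6 among the secondary endpoints. For the first, SAP 2.6.2 says that the "Kaplan-Meier estimator will be used to estimate the cumulative incidence function and the results will be plotted". The window is stated: "Only the treatment period will be included in this time to first response analysis". The time "will be considered censored at the date of the last non-missing weekly score for any patient who is a non-responder". No distinction is made between completing Week 52, stopping treatment, leaving the study and a lapse in the diary. For UAS7 ≤ 6 the section adds only a baseline exclusion, so I take the same estimator and censoring rule to apply.

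SAP 5.1 dates the end of treatment for an early stopper by the first available item in a list that begins "last dosing date + 4 weeks, last visit date, PD date of missing visit at Week 52". Protocol 9.1.1 expects such patients to go on to the follow-up visits, but those weeks then fall outside the window.

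Protocol 6.1.4 allows treatment to end for disease progression. Protocol 9.1.1 requires it for a list of reasons, one of which begins "If a subject uses rescue oral corticosteroids for CSU more than 3 doses in a 30 day period". The expected loss is in SAP 3.1: "Considering 10% drop out rate based in the QGE031C2201 study".

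Nothing visible elsewhere deals with this. The weekly responder proportions are point-in-time figures ("No non-responder imputation is planned in this study"), and the repeated-measures model in SAP 2.6.4 covers mean change only.

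**The concern.** A cumulative incidence is the proportion of a defined group who have had the event by a given time. Here the event is a first response during treatment. A patient who stops without one cannot have it later, so stopping acts as a competing event. Kaplan-Meier treats that patient as still able to respond, at the rate seen in those who remain. If stoppers are on the whole doing worse, that rate is too favourable to them.

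The trial has one arm, so no control curve carries the same distortion. The Week 52 height of the curve will be read as an absolute figure for treated Japanese patients, and any gap runs in the favourable direction.

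**Working it through.** **1. The plan's own figure.** 65 × (1 − 0.10) = 58.5; SAP 3.1 states 58. That implies 6.5 to 7 patients without a year of exposure. The SAP gives no expected height for the response curve, so response rates and timing below are assumptions.

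**2. Direction.** Let h(w) be the weekly response hazard, K(w) the Kaplan-Meier product of 1 − h, and S(w) the proportion still on treatment without response.
- Planned: 1 − KM = Σ K(w−1) h(w).
- Share responding on treatment (Aalen-Johansen): Σ S(w−1) h(w).

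S also falls with each stop, so S ≤ K, and the planned figure is never the lower one. The two are equal only if no non-responder stops before a later first response.

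**3. Hand check, N = 65.** Suppose 39 respond, 7 stop without response and 19 complete without response. The share is 39/65 = 60.0%, and Aalen-Johansen returns this in every pattern. The planned 1 − KM gives:
- all 7 leave before anyone responds: 39/58 = 67.2% (+7.2, the ceiling for this case);
- stops spread over Weeks 4–44, responses spread evenly over the year: 65.2% (+5.2);
- same stops, 70% of responses by Week 12: 63.4% (+3.4);
- stops in Weeks 36–48, 70% of responses by Week 12: 61.4% (+1.4).

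With 26 to 45 responders and stops in Weeks 4–8, 4–44 or 36–48, the excess runs from +0.6 to +8.1 points. All of these take every stopper to be a non-responder.

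**4. Expected excess at Week 52, in points.** Weekly grid, 10% stopping. Response times are exponential with mean 12 or 20 weeks, truncated at Week 52. Stops are uniform over Weeks 4–52 or 4–28. Each cell is the range over these four settings.

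| Response | Stopping unrelated to response | Half of stoppers are non-responders | All stoppers are non-responders |
|---|---|---|---|
| 50% | 0.8–2.1 | 0.6–1.5 | 1.3–3.3 |
| 60% | 0.9–2.5 | 0.8–2.0 | 1.8–4.3 |
| 70% | 1.1–3.0 | 1.1–2.6 | 2.4–5.6 |
| 80% | 1.3–3.4 | 1.6–3.3 | 3.6–7.4 |

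In the first results column the response rate is what would be seen if nobody stopped; in the other two it is the share responding on treatment. For scale, the standard error at 80% is √(0.8 × 0.2 / 65) = 5.0 points. The first two columns therefore stay below 0.7 SE, and the upper case is about 1.5 SE.

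**5. Timing.** With all stoppers non-responders and 80% response, moving the stops to Weeks 16–52 lowers the range to about 2.4–4 points. A mean response time of 6 weeks with stops over Weeks 4–52 lowers it to 1.5.

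**The case against.** Kaplan-Meier with censoring at the last score is a standard estimator of response under continued treatment, and is valid if stopping is non-informative. In the unrelated-stopping column it returns the assumed 50%, 60%, 70% and 80% to within rounding. The SAP states no estimand, so a reader might infer more than the documents support by calling the curve simply wrong. It exceeds one quantity and may be right for another.

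A reader might also infer an overstatement of seven points or so. That needs every stopper to be a non-responder, a high response rate and early stops, none of which the documents give. The steroid rule cannot produce stops before Week 12, because rescue steroids are allowed only after that (protocol 6.2.3). Protocol 6.2.2 lets a patient who used a prohibited drug give it up and continue. Several reasons in protocol 9.1.1, such as pregnancy, a live vaccine or a low platelet count, do not select for poor response.

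Nor is stopping a competing event by nature. Stoppers keep a diary in follow-up and could still reach UAS7 = 0. The window makes it one, and SAP 2.6.2 does not cite SAP 5.1; the study design sections describe the treatment period only as 52 weeks. On that looser reading a stopper stays at risk until the diary ends, and is then still censored.

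Finally, these curves are absent from protocol 12.5.1 and SAP 1.2, and nothing is tested.

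These arguments limit the size and weight of the point. They do not remove it: the label names the quantity that Kaplan-Meier does not estimate here, and the alternative target is neither stated nor defended against stopping for disease progression or excess steroid use.

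**Conclusion.** The point holds as a minor one. As planned, the curve is at or above the share of treated patients with a first response on treatment; that direction is algebraic, given the SAP 5.1 end date for early stoppers. It equals response under continued treatment only if stopping is non-informative, which protocol 6.1.4 and 9.1.1 make doubtful for some stoppers.

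At the planned N and drop-out, the excess at Week 52 is about 1 to 3.5 points at the higher response rates if stopping is unrelated to response or half of the stoppers are non-responders, and about 0.5 to 3.5 points across 50% to 80% response. About 7 points is an upper case, and the excess shrinks with faster response or later stops. All of this rests on assumed response rates and timing. No error rate, sample size or primary safety conclusion changes, and the weekly responder proportions are untouched.

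**What to change.** In SAP 2.6.2, for both UAS7 = 0 and UAS7 ≤ 6:
- State that the curve estimates the share of treated patients with a first response while on treatment, with the end of treatment taken from SAP 5.1.
- Estimate it by Aalen-Johansen, with permanent treatment discontinuation or death before response as the competing event.
- Censor completers without response at Week 52. Keep patients who are still on treatment but whose diary lapses censored at the last non-missing weekly score, so that unobserved weeks are not counted as non-response.
- Show 1 − KM alongside, labelled as response under continued treatment assuming non-informative discontinuation.

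Counting every discontinuation as competing, whatever its cause, is a choice of target, which is why the target should be written down. The cost is SAP wording and a little programming, with no new data. The downside is a slightly less favourable Week 52 figure.

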2.6.3 Handling of missing values/censoring/discontinuations

The UAS7 score is derived from the sum of the HSS7 score and the ISS7 score, as noted above. If ISS7 or HSS7 is missing, UAS7 will also be missing. The HSS7 and ISS7 score will be derived by adding up the daily HSS and ISS scores of the 7 days preceding the visit, respectively. The daily score (HSS and ISS) will be calculated by averaging the morning and evening HSS

and ISS score, respectively. If one of the morning or evening scores is missing, the non-missing score for that day (morning or evening) will then be used as the daily score.

For each weekly score from the UPDD (i.e. HSS7, ISS7), if one or more of the daily scores are missing, the following principles will be applied to handle the missing data:

- If a patient has at least 4 non-missing daily (morning or evening) scores within the 7 days prior to the study visit, the weekly score will be calculated as the sum of the available eDiary scores of that week, divided by the number of non-missing days, multiplied by 7.
- If there are less than 4 non-missing daily scores within the prior 7 days, then the weekly score will be considered as missing for that week.

Duplicate data handling of questionnaires

For HSS7, ISS7, the daily score is derived from the average of morning and evening scores (e.g. in case HSS is entered twice in the morning at different times).

All other questionnaires (i.e. other than HSS and ISS) are completed either daily or at visits. If any of those questionnaires are completed more than once per day or visit (depending on the questionnaire schedule), then the worst outcome (i.e. the highest score) of the duplicate observations will be used in the analysis.

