8.3.1 Electronic Diary (eDiary) assessments

8.3.1.1 Urticaria Patient Daily Diary (UPDD)

UPDD includes Urticaria Activity Score (UAS) which assesses twice daily the severity of itch and number of hives.

[REDACTED] section 16.4 Appendix 4, Patient Diary: Urticaria Patient Daily Diary (UPDD)). The components are presented in the [Table 8-2](#) and the relevant weekly scores are described below.

Table 8-2 Urticaria Patient Daily Diary (UPDD)

Diary component	When assessed
Urticaria Activity Score (UAS) • Itch severity • Number of hives	Morning and evening
Sleep interference	Morning
Daily activity interference	Evening
[REDACTED]	[REDACTED]

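### For the zero-score endpoints, a week with only four recorded days, all zero, counts as complete response, and a sparsely recorded symptomatic week in follow-up does not count as loss of response

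*SAP*

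**What the plan says.** The diary is completed twice a day (Protocol 8.3.1.1: "UPDD includes Urticaria Activity Score (UAS) which assesses twice daily the severity of itch and number of hives"), so a full week has 14 entries. SAP 2.6.3 then works as follows.

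- Daily score: the mean of morning and evening. With one entry absent, "the non-missing score for that day (morning or evening) will then be used as the daily score".
- Weekly score: "If a patient has at least 4 non-missing daily (morning or evening) scores within the 7 days prior to the study visit", the available sum is "divided by the number of non-missing days, multiplied by 7".
- Below that: "If there are less than 4 non-missing daily scores within the prior 7 days, then the weekly score will be considered as missing".
- Composite: "If ISS7 or HSS7 is missing, UAS7 will also be missing".

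SAP 2.6.2 sets response status from the weekly score. A zero is a response; "otherwise it is considered as a non-response unless UAS7 is missing". No non-responder imputation is planned. Time to first UAS7 = 0 uses the treatment period. Time to loss of UAS7 = 0 starts at Week 52, and subjects still in response are censored at their last non-missing weekly score.

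Protocol 8.3.1.1.1 has the same four-day threshold, but requires 14 of 14 entries in the baseline week. Neither document sets a separate completeness rule for the zero endpoints. The supportive MMRM (SAP 2.6.4) covers change from baseline only. SAP 2.1 provides a category for missing data, so it is not explicit whether the response percentages are taken over scored subjects or over the whole Safety Set.

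**The concern.** Scaling replaces an unrecorded day by the average of the recorded ones, which is a reasonable estimate of a mean. A zero endpoint is different. Daily scores cannot be negative, so a fully recorded week sums to zero only if every entry is zero. Four clear days do not establish that for seven, and scaling a zero sum leaves it at zero. Below four days the difficulty reverses: one recorded hive or itch already proves the week is not zero, yet the rule discards it.

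Protocol 8.3.4 names complete control (UAS7 = 0) as the current target of therapy. The zero status feeds the weekly proportions, time to first UAS7 = 0 (where one sparse zero week is an event) and time to loss of UAS7 = 0.

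**Working it through.** The plan states no figure on this point, so there is none to reproduce. Its only related rate is 10% missing post-baseline UAS7 (58 of 65 subjects; Protocol 12.8.2, SAP 3.2), which is not a rate per diary entry.

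**1. Test weeks under SAP 2.6.3**

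| Recorded in the week | Weekly score | Status |
|---|---|---|
| 4 single entries on 4 days, all 0 | 0 / 4 × 7 = 0 | response |
| 3 days at the maximum of 3, 4 days unrecorded | none | missing |
| 3 days at 3, 4 days at 0 | 9 / 7 × 7 = 9.0 | non-response |
| 1 day at 1, 3 days at 0 | 1 / 4 × 7 = 1.75 | non-response |

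In the first row, the ten unrecorded entries could hide an HSS7 of up to 4 × 1.5 + 3 × 3 = 15, and so a UAS7 of up to 30.

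**2. All day patterns.** Each day is zero, symptomatic or unrecorded: 3^7 = 2187 patterns.

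- Four or more days recorded, any symptomatic: 35×15 + 21×31 + 7×63 + 127 = 1744, all non-response (correct).
- Four to six days recorded, all zero: 35 + 21 + 7 = 63, all response (unproven).
- Seven days recorded, all zero: 1, response (proven).
- One to three days recorded, any symptomatic: 7×1 + 21×3 + 35×7 = 315, all missing (provably non-zero).
- None to three days recorded, no symptom: 1 + 7 + 21 + 35 = 64, all missing (undetermined).

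No truly zero week is ever labelled non-response.

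**3. Chance of a false zero.** With 4 of 7 full days recorded at random, a week with k symptomatic days scores zero with probability C(7−k, 4) / C(7, 4): 15/35 = 42.9% for k = 1, 5/35 = 14.3% for k = 2, and 1/35 = 2.9% for k = 3.

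**4. Effect on the weekly proportion (assumed inputs).** Let p be the daily symptom probability, days be independent, and a fraction f of weeks be partial, with 4, 5 or 6 days recorded equally often. Then gain = f × {mean[(1−p)^4, (1−p)^5, (1−p)^6] − (1−p)^7}.

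| p | (1−p)^7 | Mean over 4–6 days | Gain, f = 10% | Gain, f = 30% |
|---|---|---|---|---|
| 10% | 47.8% | 59.3% | 1.1 points | 3.4 points |
| 20% | 21.0% | 33.3% | 1.2 points | 3.7 points |
| 30% | 8.2% | 17.5% | 0.9 points | 2.8 points |

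If instead 40% of subjects are clear all week and the rest are symptomatic on 60% of days, the gain is f × 0.6 × (0.0133 − 0.0016), or 0.07 to 0.2 points for the same f.

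**5. Time to first UAS7 = 0.** For a subject symptomatic on half of days, independently, a truly zero week has probability 0.5^7 = 0.0078. Over 52 weeks, 1 − (1 − 0.0078)^52 = 33%. With partial weeks as in step 4, the weekly chance is 0.0107 at f = 10% and 0.0135 at f = 20%, giving 43% and 51%.

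**6. Does requiring seven days help?** Take p = 10%, with days missing at random. Among weeks with at least four recorded days, the plan's rule gives 52% response at 10% missing and 58% at 30%. Among complete weeks the rate is 0.9^7 = 47.8%, the true value.

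**7. Dropping weeks with fewer than four days.** Simulated weeks, true response 40%, missing rates varying between patients:

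| Assumed missing entries | Rate under the plan's rule |
|---|---|
| Symptom-free 10%, symptomatic 40% | 47–56% |
| Symptom-free 40%, symptomatic 10% | 33–37% |

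These ranges run over 10–60% of half-days symptomatic in non-zero weeks, and they include false zeros.

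**The case against.** The threshold is prespecified in the protocol, the documents define response as a score of zero, and efficacy here is secondary and descriptive in a single-arm safety study. All of that stands, and it limits the weight of the point. It does not answer it: on complete data a zero score means that every entry was zero, and the plan does not examine how far partial weeks depart from that.

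A reader might infer that any week with one to three symptomatic days is lost. It is not. With four or more recorded days such a week scores above zero and is a non-response, as the last two test weeks show.

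A reader might also infer that both features of the rule favour the drug. The documents do not support that for the discarded weeks. Sparse all-zero weeks are dropped too, so dropping is neutral when missingness is unrelated to symptoms and can push the proportion either way otherwise. If percentages use the whole Safety Set, dropped weeks do not inflate them. Even for time to loss, a false zero at Week 52 can admit a subject who then loses response early.

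Nor should sparse symptomatic weeks become non-responses in the main analysis. Sparse weeks would then enter the denominator only when bad. With p = 10% and 10–20% of weeks having one to three recorded days (the rest complete), a true 47.8% would be reported as 46.9% to 45.7%, while the plan's rule stays at 47.8%. In one extreme simulated case (50% of entries missing, unrelated to symptoms, varying between patients), that rule gives 34.6% against a true 40%; the plan's rule gives 40.0%.

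Finally, a sparse symptomatic week in follow-up usually delays the loss to the next scored non-zero week. It is censored only if no such week follows.

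**Conclusion.** The concern holds in two limited parts. First, accepting four to six recorded zero days as a zero week can only create false responders, in the weekly proportions for all three zero endpoints and in time to first UAS7 = 0. Second, in the time-to-loss analysis, a recorded symptom in a week with one to three recorded days is not counted, so an observed loss is delayed or censored. The effect of discarding such weeks on the weekly proportions has no fixed direction; it depends on who skips entries and on the unstated denominator.

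The size cannot be settled from the documents. About 1 to 4 points per week rests on independent days, one symptom probability for all subjects and 10–30% partial weeks; clustering of symptoms can reduce it to 0.2 points or less. The 33% to 43% or 51% figure applies only to the assumed subject symptomatic on half of days for a year. This calls for supporting analyses and one event definition, not a new main derivation.

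**What to change.** In SAP 2.6.2 and 2.6.3, keep the four-of-seven scaled scores for mean change and as the main responder derivation, and add:

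1. A sensitivity analysis for the zero-score proportions and time to first UAS7 = 0, in which a week is a response only if all seven daily scores are recorded and zero. For the proportions, leave every incomplete week unclassified, symptomatic or not, so that the analysis is not lopsided.
2. In time to loss of UAS7 = 0, count any week with a recorded non-zero itch or hives entry as a loss, however many days are missing. The weekly score itself can stay missing.
3. For the weekly proportions, a lower-bound analysis that treats sparse symptomatic weeks as non-response, labelled as a bound.

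State the denominator of the percentages as well.

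The cost is SAP wording and a derivation flag; no new data are needed. Figures will be slightly less favourable. The sensitivity analysis will classify fewer weeks: with days missing independently, 0.9^7 = 48% of weeks are complete at 10% missing, but only 0.7^7 = 8% at 30%. It also does not remove the single-entry allowance, since seven daily scores may still rest on seven of 14 entries; the report should say so.
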